2 STUDY OBJECTIVES AND OUTCOMES

2.1 Study objective

The primary objective of this study is to establish the feasibility of collecting emergency department (ED) visit data among the PWD cared for by the primary care practices. The secondary objective of this study is to measure short term impacts of the adapted Care Ecosystem training on PWD and their caregivers.

2.2 Primary outcome measure

The primary outcome is the change in ED visits per member per month from the 12 months prior the adapted Care Ecosystem training to the 6 months post training.

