Interviews will be scheduled two months after the launch of the CareEco training (month five). These interviews will be conducted in care manager offices or by telephone or a video technology platform at the convenience of the care manager. The interviews will last approximately 30 to 40 minutes. Research with the iCMP care management staff, conducted by our team in both 2017 and 2018 as part of a PCORI funded study of care management programs, achieved 75% participation rates. Interview domains will include 1) general experience in caring for PWD and their caregivers; 2) experience in direct outreach to caregivers and patients (including identifying the most knowledgeable or engaged caregivers); 3) perceptions of services most needed and most difficult to arrange for patients with dementia and their caregivers; 4) assessment of the adequacy of training as adapted to the iCMP context; 5) recommendations for further adaptation of the CareEco model, and 6) among care managers not participating in the training, implementation

barriers, including contextual factors, fit and overarching issues that impacted non-participation.

The following table summarizes the measures that will be used in this study.

Variable	Source	Primary or secondary outcome	Description
ED visits	Medicare Claims data	Primary	ED visits per member per month over 6 months; Feasibility of collection (Primary objective), difference between early and delayed cohorts (secondary objective)
Service utilization and costs	Medicare Claims data	Secondary	Hospitalizations, Observation stays, urgent visits, total medical expense; Feasibility of collection (Primary objective), difference between early and delayed cohorts (secondary objective)
Documentation of advance care planning	Epic	Secondary	
Documentation of medication review and reconciliation	Epic	Secondary	
Caregiver Depression *	Caregiver survey	Primary and Secondary	PHQ-8 (8 item)
Caregiver strain and burden *	Epic	Primary and Secondary	Caregiver Strain Index presence in Epic and magnitude
Caregiver strain and burden *	Caregiver survey	Primary and Secondary	Zarit Rating Scale (12-item) 
Behavioral Symptoms of Dementia *	Epic and Caregiver survey	Primary and Secondary	NPI-Q (Neuropsychiatric inventory Questionnaire)  presence in Epic and magnitude
PWD quality of life	Caregiver survey	Secondary	QOL-AD (13 items) 

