### **9.3 Outcomes**

The primary outcome for the is pilot is emergency room visits within 6 months. We will rely on Epic and Medicare claims data for all measures of healthcare service utilization and costs, care intensity / quality, documentation of advance care planning, and documentation of medication review. These outcomes will be assessed for all PWD who are cared for by selected nurse care managers using retrospective analysis of existing health care data. We anticipate that this will include 150 PWD among care managers who receive early training and 150 PWD who receive delayed training. These data are housed in an existing data repository; we anticipate minimal missing data. Key secondary outcomes will assess the number of contacts between nurse care managers and care partners, and documented advance care planning; these measures likewise available from the existing data warehouse and we anticipate minimal missing data.

In order to ensure systematic capture of key clinical outcomes within this pilot, we will survey caregivers of PWD receiving care management from the 30 selected nurse care managers and meeting our inclusion and exclusion criteria at months 3 and 9. We expect that a minimum of 50% of caregivers will complete each survey, yielding an expected sample of 75 PWD caregiver respondents completing each survey and 37 PWD caregiver respondents completing both an initial and follow- up survey for nurses assigned to the early and the delayed training. We will assess the completeness and correlation of behavioral symptoms of dementia, caregiver depression, caregiver burden, and PWD quality of life captured via trained nurse care managers (and documented in Epic or iCMP data) with caregiver survey responses.

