7 GENERAL ANALYSIS CONSIDERATIONS

7.1 Analysis populations

7.1.1 Utilization Outcome Cohort

For ED visit outcome measurement, the validated cohort was then further restricted to those with at least 1 member month of Medicare FFS eligibility and alignment to our ACO in the pre and the post period (Intervention n=126, Control n=105), to allow for sufficient utilization data for measurement. (See Figure 1 of cohort flowchart)

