8 STATISTICAL ANALYSES

8.1 Primary outcome analysis

The change in ED visits PMPM from 12 months prior to training to 6 months post-training for intervention and control cohorts are compared using a differences-in-differences model with a negative binomial distribution (to account for utilization count data) and log link. This model estimates a difference-in-differences rate ratio that provides an estimate of the relative rate reduction/increase in ED visits PMPM in the intervention group as compared to controls.

Models included a weight for the number of member months in the pre and post periods, allowing PWD with more member months (and therefore more stable estimates) to contribute more strongly to the intervention effect. The training (“enrollment”) month was not included in either pre or post period. Models adjusted for baseline utilization and demographic characteristics (race, ethnicity, age) that differed across intervention and control cohorts. A sensitivity analysis removed PWD who died in the post period.

We hypothesized high feasibility in measuring ED visits for this population but had no specific hypothesis regarding whether the program would impact ED utilization in the relatively short 6 month-post period.

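### The SAP's primary objective is feasibility of collecting ED data, but its only primary analysis is a between-arm ED rate ratio that the protocol assigns to the secondary objective; no feasibility quantity is estimated

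*SAP*

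**What the plan says.** SAP 2.1 sets the order of objectives. First: "The primary objective of this study is to establish the feasibility of collecting emergency department (ED) visit data among the PWD". Second: "The secondary objective of this study is to measure short term impacts of the adapted Care Ecosystem training on PWD and their caregivers". Protocol 1.1, 3 and 9.1 agree that feasibility comes first. In the measures table of Protocol 6, the ED row divides the roles explicitly: "Feasibility of collection (Primary objective), difference between early and delayed cohorts (secondary objective").

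SAP 2.2 then defines the primary outcome differently: "The primary outcome is the change in ED visits per member per month from the 12 months prior the adapted Care Ecosystem training". The other side of that change is a 6-month period afterwards. SAP 8.1 compares this change between arms with a negative binomial difference-in-differences model and reports a rate ratio. The only feasibility text in that section is one sentence: "We hypothesized high feasibility in measuring ED visits for this population". The same sentence says there was no specific hypothesis about an effect on ED use.

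The ratio is fitted in the cohort of SAP 7.1.1, limited to PWD with "at least 1 member month of Medicare FFS eligibility and alignment to our ACO in the pre and the post period". The reason given is that there should be enough utilization data to measure.

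Protocol 9.3 calls the pilot's primary outcome "emergency room visits within 6 months", and the measures table gives it per member per month over 6 months.

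**The concern.** The objective, the outcome and the analysis do not line up. The quantity with a hypothesis (feasibility) has no metric, denominator, interval or criterion. The quantity with a full model (the arm contrast) has no hypothesis and serves the secondary objective. Protocol 9.4 does not fill the gap, because it lists only models of the intervention effect.

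The analysis set adds to the problem. It is selected on having member months in both periods, so anyone looking only at the analysed PWD will find that ED data could be obtained for all of them.

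Protocol 9.2 says the pilot is meant to show whether measurement is feasible and to supply effect-size data for a full-scale study. Followed as written, the SAP delivers the second and leaves the first to be inferred from cohort counts, against a denominator each reader must choose.

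**Working it through.** **Inputs, all from SAP 6 and 7.1.1 (intervention + control)**

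- Planned: 30 nurses × 10 PWD = 300, which matches the stated figure. There is no power or precision calculation to reproduce.
- Met the inclusion criteria: 206 + 187 = 393.
- Validated cohort: 143 + 113 = 256.
- ED analysis cohort: 126 + 105 = 231.

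**Step 1. Inside the analysed cohort.** Having at least one member month in each period is the entry rule, so the proportion is 231/231 = 100% by definition. This covers having some data only. The rule admits a PWD with 1 of 12 pre months and 1 of 6 post months, so completeness is not guaranteed and could have been reported.

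**Step 2. Before the restriction, in the validated cohort.** The proportion is x/n with a Wilson 95% interval, ignoring clustering by nurse.

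- Overall: 231/256 = 90.2% (86.0 to 93.3). The exact interval is 85.9 to 93.6.
- Intervention: 126/143 = 88.1% (81.8 to 92.4), a loss of 143 − 126 = 17 (11.9%).
- Control: 105/113 = 92.9% (86.6 to 96.4), a loss of 113 − 105 = 8 (7.1%).

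The arms differ by 92.9 − 88.1 = 4.8 percentage points (Fisher exact p = 0.21). That does not establish differential loss, but a feasibility analysis would report it.

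**Step 3. Among those meeting the inclusion criteria.** 231/393 = 58.8% (53.8 to 63.5). By arm, 126/206 = 61.2% and 105/187 = 56.1%. This is a lower bound. The 393 − 256 = 137 PWD removed include some who had died or moved to a skilled nursing facility, and some of these may be ineligible under SAP 4.2. Others had no designated caregiver, which is not a PWD exclusion in SAP 4.2 and is unrelated to claims. Their claims status is not given. If all 137 were eligible and measurable, the figure would be (231 + 137)/393 = 368/393 = 93.6%. On the both-periods definition, the counts therefore allow anything from 58.8% to 93.6%.

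**Step 4. Does the criterion matter?** The documents give no threshold, so these are assumptions.

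| Assumed threshold | 231/256, point estimate | 231/256, lower limit |
|---|---|---|
| 80% | met | met |
| 85% | met | met, by about 1 point |
| 90% | met | not met |
| 95% | not met | not met |

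Allowing for clustering within 30 nurses would be expected to widen the interval, so the 85% result on the lower limit is not secure.

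**Step 5. The ED measure.** Protocol 6 and 9.3 describe visits over 6 months. SAP 2.2 describes a change from a 12-month pre-period. The post window is 6 months in both; the difference is whether the baseline is part of the outcome.

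**The case against.** The best defence is that the protocol is itself mixed. Section 9.3 names ED visits as the primary outcome, section 9.1 calls them the primary clinical outcome, and the measures table marks the variable as primary. This stands. A reader might infer that the SAP overturned a clear protocol rule. It did not: it took one side of an existing ambiguity. What the protocol does not support is making the arm contrast the sole primary analysis, because the measures table places that contrast under the secondary objective. SAP 2.2 on its own also describes only a pre-to-post change; the between-arm comparison enters in SAP 8.1.

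Second, the SAP reports 393, 256 and 231 by arm, so a rough feasibility figure can be worked out. This also stands, and it rules out the inference that the trial cannot address its primary question. The gap is an unspecified measure, denominator and criterion.

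Third, 58.8% might be read as the share of PWD whose ED data could be collected. The documents do not support that, for the reasons in Step 3 of the working.

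Fourth, an effect estimate without a directional hypothesis fits a pilot that is meant to inform effect sizes. Agreed: the contrast belongs in the SAP, under the right objective.

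**Conclusion.** The concern holds. The SAP's primary outcome and primary analysis serve its secondary objective, and the feasibility it hypothesises is never estimated. This is more than missing detail, because a training-impact ratio would be reported as the primary result, from a set already selected on data availability.

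The best available figure is 90.2% of the validated cohort (Wilson 95% CI 86.0 to 93.3). It rests on three assumptions: measurable means at least one member month in each period, the 256 are the right denominator, and nurse clustering is ignored. A definition based on the post window alone could only raise the numerator, since some of the 25 lost (256 − 231) may have lacked only pre-period months.

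Two stronger readings are not supported. Feasibility is not wholly met by construction, because month-level completeness among the 231 remains open. Nor do the documents show that difference-in-differences is the wrong model for the ED contrast; replacing it with a baseline covariate would be a preference.

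**What to change.** In SAP 2.2 and 8.1:

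1. Define the primary feasibility measure before the SAP 7.1.1 restriction, as the proportion of eligible PWD with ED data in the post window. Eligible means the 393 less those meeting the SAP 4.2 exclusions, with the 256 shown alongside. Protocol 9.3 planned the claims outcomes for all PWD of the selected nurses, so the wider denominator is the natural one.
2. Add observed member months out of 6, or out of months alive.
3. Report both overall and by arm, with a nurse-clustered 95% CI.
4. State the criterion for calling collection feasible. The SAP already reports realised cohorts, so label the measure and criterion post hoc if they are set after the data were seen.
5. Label the between-arm ED comparison as a secondary-objective analysis, as in the protocol's measures table.
6. Reconcile the ED definitions in Protocol 6 and 9.3 with SAP 2.2. No particular change of model is required.

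The cost is SAP wording and one descriptive table. Member months are already used as weights in SAP 8.1, and deaths in the post period are already identified for its sensitivity analysis. Member months for the eligible PWD among the 137 would also be needed; whether they are already to hand cannot be told from the documents, because the flowchart is not shown.

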2.3 Secondary outcome measure

The secondary outcome is the change in caregiver distress between baseline and 6-month follow-up survey. Caregiver distress is measured by the Neuropsychiatric Inventory Questionnaire (NPI-Q), a brief proxy/caregiver-report of patient severity and caregiver distress across 12 neuropsychiatric symptom domains. Scores on the NPI-Q Distress scale can range from 0 to 60. The NPI-Q has demonstrated reliability and validity in dementia patients.

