### Objectives

Our primary objective is to test the feasibility of collecting emergency department visit data among the PLWD cared for by the primary care practices.

Our secondary objective is to determine the short-term impacts of an adapted Care Ecosystem curriculum and workflow on care management processes, healthcare utilization, behavioral symptoms of dementia, caregiver burden, and caregiver depression.

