The Care Ecosystem (CareEco) model uses a telephone-based intervention to support persons with dementia (PWDs) and their caregivers, screening for common dementia-related problems and providing modular standardized support protocols and caregiver education. Specially trained health care navigators systematically identify needs and address health status, advance care planning, medication management and management of challenging behaviors. Health care navigators receive backup support from a nurse,

social worker, dementia specialist, and pharmacist, and maintain close communication with the primary care provider of the PWD. CareEco was found to reduce ED utilization, improve PWD quality of life and improve caregiver outcomes. While the healthcare navigators used in CareEco offer clear value, this model, if adopted in a system with established, robust care management teams and no preexisting health care navigators, could actually increase cost by adding personnel in the setting of limited space and resources. We hypothesize that adapting the CareEco model to augment the dementia care provided by a pre-existing care management team could improve care manager self-efficacy in supporting PWDs, improve outcomes for PWDs and their caregivers, and optimize sustainability by enhancing dementia care competency of existing clinicians. In the proposed pragmatic clinical trial pilot, we will develop and test an adapted form of the CareEco intervention with experienced Integrated Care Management Program (iCMP) nurse care managers engaged in the care of high-risk, high-cost patients in a large health system. The strategic priorities of our health system are aligned with this work, both as a tool to provide higher-quality care to a high-risk population and as an opportunity to reduce ED visits and avoidable costs.

The integrated care management program (iCMP) at Partners HealthCare is a nurse-led longitudinal care management program embedded in Primary Care practices across the Partners network that provides care management support to the most medically complex and seriously ill patients. iCMP care managers assess each patient to clarify problems, identify barriers to accessing clinical care and community-based services, including the social determinants of health, and create a patient-centric care plan. The iCMP program serves all payor populations and has cared for over 38,000 patients since 2012.

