#### 6.2.3 Follow Up/Final Evaluation

Refer to “Baseline Assessments” for a description of the assessments that will be used to collect data from PWDs/caregivers at both baseline and follow-up.

**Medicare claims data** will be used to construct measures of health care utilization and costs. This data will be accessed in months eight and nine.

**Epic clinical data** will be used to capture PWD and caregiver outcomes documented in the iCMP note and to identify whether medication reconciliation and serious illness conversations/advance care planning occurred related to the iCMP interaction. In addition, Epic elements flow to tables within the Partners data warehouse.

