### **9.4 Data Analyses**

Depending on the type of outcome, we will conduct either a linear, negative binomial, or logistic regression, with random effects for nurses, to account for multiple patients nested within the same nurse. The primary predictor will be intervention (iCMP nurse care manager assignment to early CareEco training versus delayed training). Models will be adjusted for a limited number of baseline covariates: dementia stage and severity; Elixhauser score; and patient characteristics. If there are many unbalanced patient or

nurse characteristics, we will use propensity score weighting to adjust for confounding in the face of the limited sample size. Secondary models will examine process measures as potential mediators of the intervention effect on reported outcomes, clinical outcomes, and utilization outcomes. Subgroup analyses will be explored, but given the limited sample size, we do not expect sufficient power to detect effect modification nor significant intervention effects within subgroups.

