7.2 General considerations for statistical analysis

Data are summarized by treatment group. Continuous variables are summarized using mean and standard deviations. Categorical variables are summarized using frequency and percentages. SAS Enterprise Guide 7.1 is used for analyses.

Demographic and other baseline characteristics are compared between groups. Race, ethnicity, age, gender, language, marital status, baseline primary care provider (PCP) utilization per member per month (PMPM), baseline inpatient utilization PMPM, baseline ED utilization PMPM, and baseline observation visits PMPM are summarized for the Utilization Outcome Cohort. For the Clinical Outcome Cohort, the same characteristics will be summarized, as well as NPI-Q Distress (caregiver distress), NPI-Q Severity (patient symptom severity), PHQ-8 (caregiver depression), and Quick Dementia Rating Scale (patient dementia severity) from the baseline survey.

A combination of t-tests (at $p < .05$), chi square tests (at $p < .05$) and standardized mean differences (cutoff of .15 or greater) were used to identify differences between cohorts and covariates for risk adjusted models. Based on these criteria, race, ethnicity, and age were identified as different between intervention and control in the Utilization Outcome Cohort, as were baseline PCP visits, inpatient hospitalizations, and Observation visits. For the Clinical Outcome Cohort, PHQ-8 (caregiver depression) was different across Intervention and Control. Risk adjusted models for clinical outcomes also adjusted for the demographic characteristics (race, ethnicity, and age) identified for the risk adjusted utilization models in order to maintain consistency across models.

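### The SAP keeps ED visits as its only utilization outcome and omits, without a reason, the protocol's between-arm comparison of hospitalizations, observation stays, urgent visits and total medical expense

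*SAP*

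**What the plan says.** **Protocol.** The secondary objective in the Précis covers "care management processes, healthcare utilization, behavioral symptoms of dementia, caregiver burden, and caregiver depression". In the section 6 measures table, the claims-based row below ED visits is marked secondary and described as "Hospitalizations, Observation stays, urgent visits, total medical expense; Feasibility of collection (Primary objective), difference between early and delayed cohorts (secondary objective". Section 6.2.3 says Medicare claims "will be used to construct measures of health care utilization and costs". Section 9.4 supplies a model for every outcome type: "Depending on the type of outcome, we will conduct either a linear, negative binomial, or logistic regression, with random effects for nurses". The background gives part of the motivation "as an opportunity to reduce ED visits and avoidable costs".

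**SAP.** Section 2.2 states "The primary outcome is the change in ED visits per member per month", measured from the 12 months before training to the 6 months after. Section 2.3 is in the singular: "The secondary outcome is the change in caregiver distress between baseline and 6-month follow-up survey". Sections 8.1 and 8.2 model these two outcomes and no others. Other acute care enters in section 7.2, where "baseline inpatient utilization PMPM, baseline ED utilization PMPM, and baseline observation visits PMPM are summarized for the Utilization Outcome Cohort". That section also reports that baseline hospitalizations and observation visits differed between the arms, and section 8.1 then adjusts for baseline use. The SAP does not say that the remaining claims outcomes were withdrawn, deferred or reported elsewhere.

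**The concern.** A secondary objective that names healthcare utilization, with four claims measures listed under it, should lead to an analysis of those measures. In the SAP it leads to ED visits only. Three things are lost.

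- The protocol's utilization and cost comparison is left unanswered, although cost is part of the stated motivation.
- Protocol 9.2 justifies the pilot partly by the effect-size data it will give a later full-scale trial. For these four outcomes there would be none.
- The ED rate ratio would stand without context. A reader could not see whether admissions, observation stays or urgent visits moved the same way, the opposite way or not at all. Adjusting for baseline inpatient and observation use does not supply this, because it says nothing about the period after training.

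The same table row also places the feasibility of collecting these measures under the primary objective, so leaving them out touches the feasibility question as well.

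**Working it through.** **Step 1. Set the outcome lists side by side.**

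| Claims measure | Protocol section 6 table | SAP |
|---|---|---|
| ED visits per member month | Primary; feasibility and between-arm difference | Primary outcome (2.2), modelled (8.1) |
| Hospitalizations | Secondary; feasibility and between-arm difference | Baseline descriptor and covariate only (7.2, 8.1) |
| Observation stays | As above | Baseline descriptor and covariate only (7.2, 8.1) |
| Urgent visits | As above | Not mentioned |
| Total medical expense | As above | Introduction only; never an outcome |

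Four of the five claims measures with a planned between-arm comparison have no analysis. The only sensitivity analysis for ED visits removes people who died, so it does not fill the gap.

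**Step 2. Reproduce the plan's own figures.** The planned size is 30 nurses × 10 PWD = 300, or 15 × 10 = 150 per arm, as stated. The SAP's achieved counts add up to 206 + 187 = 393 meeting the inclusion criteria, 143 + 113 = 256 validated, and 126 + 105 = 231 in the Utilization Outcome Cohort. There is no power calculation to reproduce, and restoring the outcomes changes none of these figures.

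**Step 3. How precise would the restored estimates be?** The documents give no event rates, dispersion or intracluster correlation, so these are assumptions:

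- hospitalization rate r = 0.02 to 0.08 per member month;
- negative binomial dispersion k = 0 to 1;
- design effect DE = 1 to 1.35. At 231/30 = 7.7 PWD per nurse and equal panels, 1.35 corresponds to an intracluster correlation of 0.35/6.7 = 0.052;
- a full 6 months for all 126 and 105 PWD.

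For a post-period rate ratio, with μ = 6r:

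SE² = DE × (1/μ + k) × (1/126 + 1/105), where 1/126 + 1/105 = 0.01746.

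The 95% interval is the estimate divided and multiplied by exp(1.96 × SE).

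| r | k | DE | SE | Factor |
|---|---|---|---|---|
| 0.08 | 0 | 1 | √(2.083 × 0.01746) = 0.191 | 1.45 |
| 0.04 | 0 | 1 | √(4.167 × 0.01746) = 0.270 | 1.70 |
| 0.04 | 1 | 1.35 | √(1.35 × 5.167 × 0.01746) = 0.349 | 1.98 |
| 0.02 | 1 | 1.35 | √(1.35 × 9.333 × 0.01746) = 0.469 | 2.51 |

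SAP 7.1.1 requires only one member month in each period, so real exposure is at most what is assumed here, and shorter exposure widens the interval. The formula also leaves out error in the pre-period rates that a difference-in-differences estimate uses. The factors are therefore a guide to order of magnitude. No cost precision can be computed, because no standard deviation is given.

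**The case against.** **It is a feasibility pilot.** The primary objective is whether ED data can be collected, and SAP 8.1 states no hypothesis about the direction of any ED effect. This limits the weight of the point but does not remove it. SAP section 3 describes a trial of feasibility and effectiveness, SAP 2.1 keeps short-term impact as an objective, and 8.1 estimates a between-arm rate ratio.

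**The extra estimates would be too imprecise to settle anything.** The imprecision is real, as Step 3 shows. It is a reason to call the estimates descriptive, not a reason to drop protocol outcomes without comment.

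**Other outcomes are missing too.** This is correct. Protocol 9.1 and 9.3 name nurse contacts and documented advance care planning as secondary outcomes, and the section 6 table adds PHQ-8, the Zarit scale and QOL-AD. None is modelled in SAP section 8. The same reconciliation is due for them. The claims outcomes are a clear case because they can share the ED analysis's cohort, windows and model family.

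**The data may not be ready.** The SAP shows inpatient and observation variables for baseline only. It does not show that post-training versions, urgent visits or cost have been built, and neither document defines an urgent visit. Some construction work has to be allowed for.

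**A stronger reading that does not hold.** A reader might infer that a fall in ED visits would really be care moved to direct admission, observation or urgent visits, so that the ED result cannot be interpreted. Neither document describes such diversion. Protocol 2.1 and SAP section 1 treat ED visits and hospital admissions as avoidable together. SAP 8.1 describes its rate ratio only as a change in ED visits, not as avoided acute care or savings. Any figure for rerouted visits would be assumption throughout. A composite acute-care endpoint does not follow either: it is not a protocol outcome, and neither document says how to count an ED visit that ends in admission or observation.

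**Conclusion.** The point holds as a gap between protocol and SAP. Four claims-based secondary outcomes with a planned early-versus-delayed comparison have no analysis and no stated reason for removal. This rests on comparing the two outcome lists and on no assumed number. The consequence is a secondary objective only partly answered, no effect-size estimates for four outcomes, and an ED result reported without the other acute care around it.

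It does not invalidate the ED model, which can answer its own question. Nor does the SAP analyse ED visits to the exclusion of everything else, since caregiver distress is also modelled. A reader might suspect that outcomes were dropped because of their results, but nothing in the documents shows that.

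The gain from the fix is descriptive: interval factors of about 1.45 to 2.5 for a hospitalization rate ratio, conditional on the rates, dispersion, design effect and full follow-up assumed above.

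**What to change.** Add to SAP 2.3 and section 8:

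1. Between-arm estimates with 95% confidence intervals for inpatient admissions, observation stays, urgent visits and total medical expense per member month, in the Utilization Outcome Cohort, over the same pre and post windows as ED visits.
2. For the three counts, the same model structure as SAP 8.1, leaving an outcome's own baseline rate out of its covariate list because the pre-period already carries it. For cost, a mean difference. In all four, account for clustering by nurse, as Protocol 9.4 specifies; SAP 8.1 as written mentions no nurse term.
3. A claims definition of an urgent visit, and a statement of whether an ED visit ending in admission or observation counts as an ED visit.
4. The label secondary and descriptive, with no power claim, and a commitment to report these estimates beside the ED result.
5. A list of any protocol outcome not restored, with the reason.

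These are outcomes the protocol already names, so restoring them creates no new endpoint. The cost is a few more models and some variable construction from claims that Protocol section 6 places in the existing data warehouse. No new data collection is planned for. The downside is more secondary estimates, each with a wide interval.
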